5.6.4 Transition between steps

A suspension of inclusions is planned between la phase II and la phase III results of la phase II analyzed.

Inclusions between the 2 stages of la phase III will not be suspended for the time of the interim statistical analysis.

5.7 Judgement criteria for la phase II

5.7.1 Main criterion

The primary endpoint of la phase II is the rate of bleeding and/or severe liver failure within one week of chemoembolization sessions (TACE), over all chemoembolization sessions for a patient. The precise definition of bleeding and liver failure to be retained is given in the protocol with amendment 3 :

- Severe liver failure is defined by the occurrence of at least one of the following complications:
 - encephalopathy;
 - clinical ascites; in case of clinical ascites already present at inclusion and persistence of ascites at the time of evaluation for liver failure, an independent committee will have to judge from the case report whether ascites has evolved since inclusion and should be counted as an event in the definition of the primary endpoint or not; if clinical ascites is present at inclusion, it will be graded according to NCI-CTC v4 and reported through a CID; during follow-up, clinical encephalopathy and ascites will be graded according to NCI-CTC v4 and will appear on form 3.1 of the case report form in the other toxicities tab
 - bilirubin levels greater than or equal to 50 mg/L (85.5 μ mol/L);
 - TP \leq 40%;
- bleeding : (definition p14 of the protocol)

These events count as primary endpoints if they occur within 1 week of chemoembolization, i.e., between D0 and D7 inclusive.

In the case of an event counting for the primary endpoint after D7, it will be recorded in the case report form 3.1 in the column after D5 only if the investigator considers that this event is related to the TACE, and the day must then be filled in. For events recorded after D7 in the case report form, an independent committee will meet to decide whether or not this event counts in the definition of the primary endpoint.

Patients who did not receive their oral treatment will still be counted in the primary endpoint; however, a very precise description of the reason for not taking the oral treatment will be made.

Patients who did not have chemoembolization will be excluded from this analysis (modified ITT).

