XVI. STATISTICAL METHOD

PILOT step

During this stage, patients will not be randomized and will all receive sunitinib. After a total of 10 chemoembolization sessions, inclusions will be discontinued and tolerance results will be reviewed by a committee of independent experts.

Patients included in this pilot phase will be particularly monitored for the purpose of detecting two potential complications associated with the combination of sunitinib- chemoembolization: severe bleeding and liver failure. The observed rate of bleeding or liver failure after chemoembolization is in the order of 10 to 15% in recent studies . One or two toxicities are expected among the 10 chemoembolization sessions. If 4 or more toxicities occur, then the toxicity of the sunitinib-chemoembolization combination is considered unacceptable and the trial is discontinued. If 3 or fewer toxicities occur, the toxicity is considered acceptable and the trial is continued in phase II with randomization. Patients included in the pilot phase will not be included in the final analysis of the SATURN trial.

The results of the pilot phase will be sent to AFFSAPS for information.

Phase II step

Patients included during this first step will be specially monitored for the detection of two complications: severe bleeding and liver failure (as defined above) in the sunitinib arm. The expected rate of severe haemorrhage and/or liver failure in patients undergoing TACE is approximately 10 % to 15%, as observed in recent studies with a TACE alone arm (25). We defined the unacceptable toxicity rate as 30 % in patients undergoing TACE plus sunitinib treatment.

Using Fleming one step design with the following hypotheses:

H0: An occurrence rate of bleeding or liver failure 1 week after last administration of the TACE-sunitinib combination of 30 % is unacceptable

H1: An occurrence rate of bleeding or liver failure 1 week after last administration of the TACE-sunitinib combination of 15% is expected

It would be required to include 35 patients in each arm.

Among the 35 patients in the Sunitinib arm:

If we observed 8 or more than 8 patients (22.9 %) with severe bleeding or liver failure 1 week after last administration of the TACE-sunitinib, the toxicity rate is not statistically different from 30%. This treatment would be declared unacceptable and inclusions will not be pursued for phase III trial.

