Two interim analyses are planned to reject H0 or H1. The p value will be done according to East software (Version 5). Using the alpha-spending function (Lan and DeMets, 1983) and O'Brien-Fleming method (O'Brien and Fleming, 1979).

The first interim analysis is planned at the final analysis (9 to 10 months after the inclusion of the first patient) of the phase II study with an expected number of events equal to 10 deaths representing 8 % of the total number of deaths required for the final analysis.

The second interim analysis is planned 34 months after the inclusion of the first patient with an expected number of events equal to 80 deaths representing 2/3 of the total number of deaths required for the final analysis

Overall survival: Time interval between randomization and death (all causes). Alive patients will be censored at the last follow-up

Relapse-free survival: Time interval between randomization and local or distant relapse or death (all causes). Alive patients without relapse will be censored at the last follow-up. Alive patients with secondary cancer will be censored at the last follow-up

Disease-free survival: Time interval between randomization and local or distant relapse or second cancer or death (all causes). Alive patients will be censored at the last follow-up.

An analysis plan will be produced before the database is frozen. All of the analyses will be conducted with a 5% (bilateral) type one error. Analyses of the principal and secondary objectives will be conducted on an intent-to-treat basis and will bear on all of the patients enrolled:

The data for each arm will be presented as means (standard deviation), median and range or percentages and will be compared using the Student t test, Anova or Kruskal Wallis and Wilcoxon for quantitative variables or the Chi 2 and Fisher exact test for qualitative variables.

Median follow up will be calculated according to the so-called « reverse Kaplan Meier » method for each of the Arms, with its 95% confidence interval.

Survival curves will be estimated using the Kaplan-Meier analyses from time to randomization, and compared by the log-rank test and stratified log rank test. Cox proportional hazard models will be used to estimate univariate and multivariate hazard ratios (HR) with 95 % confidence intervals (CI).

The incidence rate of the side effects and of the unexpected serious side effects will be reported using frequencies and percentages for:

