- Number and percentage of patients with at least one side effect
- Number and percentage of patients with at least one grade 3-4 side effect
- Number and percentage of patients with at least one SAE
- Number and percentage of patients with at least one side effect and grade 3-4 side effect due to the treatment.
- Number and percentage of patients with at least one side effect that lead to cessation of the treatment

Time to the first occurrence of grade 3-4 toxicity will be estimated by the Kaplan-Meier method.

XVII. POPULATIONS FOR ANALYSIS

The populations for the analysis are defined as follows:

Intention to treat: The intention to treat population will be composed by all included patients who were randomised to one of the two treatment groups, and patients will be analysed according to the treatment to which they were randomised. This will be the primary population for all analyses of efficacy data and baseline characteristics.

Per protocol: The per protocol population excludes patients randomised who did not receive any trial medication or who had a major violation of the protocol inclusion or exclusion criteria. Patients will be analysed according to the treatment to which they were randomised.

Safety: The safety population will include all patients who received at least one dose of trial medication. Only patients with clear documentation that no trial medication was received may be excluded. Patients will be analysed according to the treatment, which they actually received. This will be the population for the analysis of all safety data.

XVIII. ADVERSE EVENT REPORTING

1. Definition

An adverse event (AE) is defined as any untoward medical occurrence in a patient or clinical investigation subject administered a pharmaceutical product, which does not necessarily have a causal relationship with this treatment. An AE can therefore be any unfavourable and unintended sign (including an abnormal laboratory finding), symptom, or disease temporally associated with the use of a medicinal (investigational) product, whether or not related to the medicinal (investigational) product.

AE include the following:

- All suspected adverse medication reactions,
- All reactions from medication overdose, abuse, discontinuation, sensitivity, or toxicity.
- Apparently unrelated illnesses, including the worsening of a pre-existing illness.

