5.6.2 Phase II

At the end of the 35 patients/arm inclusions of the phase II:

- if the number of patients with severe toxicity (liver failure, bleeding) in the sunitinib arm is less than or equal to 7, the trial will be continued in phase III;
- if the number of patients with severe toxicity (liver failure, bleeding) in the sunitinib arm is greater than or equal to 8, the number of complications (liver failure, bleeding) in the placebo arm should also be considered:
 - if the complication rate (liver failure, bleeding) in the placebo arm is greater than or equal to 8, an independent committee of experts will have to judge the appropriateness of continuing the trial in phase III since the toxicity in the sunitinib arm may be related to the "background noise" of the toxicity of chemoembolization alone;
 - if the complication rate (liver failure, bleeding) in the placebo arm is less than or equal to 7, the independent expert committee will have to judge whether to stop the trial.

The decision rules will apply only to the sunitinib/chimio/embolization arm; the placebo/chimio/embolization arm will be maintained in all cases for la phase III, if it occurs, with this arm serving as the control arm.

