6.1.2 Modified intention-to-treat population (mITT)

The modified IIT population is defined as all patients included in the study, regardless of eligibility criteria and amount of treatment taken who had at least one chemoembolization.

The primary endpoint will be assessed in this population.

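### The phase II limit of 7 events is fixed for 35 patients, but only patients who had TACE are assessed and none are replaced, so the false-go risk passes 13.3% as soon as one sunitinib-arm patient has no TACE

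*SAP*

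**What the plan says.** **The rule.** Protocol XVI (Phase II step) uses a one-step Fleming design with 35 patients per arm, an unacceptable rate of 30% and an expected rate of 15%. It gives a calculated power of 85.6% and a type I error of 13.3%. SAP 5.6.2 applies the limit once 35 patients per arm have been included: if the number of patients with severe toxicity "in the sunitinib arm is less than or equal to 7, the trial will be continued in phase III". The independent committee is asked only when the count is 8 or more.

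**Who is counted.** SAP 5.7.1 states "Patients who did not receive their oral treatment will still be counted in the primary endpoint" and, a sentence later, "Patients who did not have chemoembolization will be excluded from this analysis (modified ITT". SAP 6.1.2 defines this modified ITT set as patients with at least one TACE and adds "The primary endpoint will be assessed in this population".

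**What is absent.** The 35 is not inflated for patients who cannot be assessed. No rule replaces a patient without TACE, and no limit is given for any number other than 35. Phase III, by contrast, carries a 5% allowance for losses (Protocol XVI, SAP 5.5.3).

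**The concern.** The rule is triggered by the number included, but the events are counted among the number who had TACE. If the second is smaller than the first, the limit of 7 is applied to fewer patients than it was calculated for. A combination with an unacceptable event rate then passes more easily.

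The SAP foresees such patients. It excludes them in 5.7.1 and plans a listing of the reasons why TACE was not done in 8.5.1.1. They can arise after inclusion, because the drug starts 7 to 10 days before TACE and angiography must first exclude significant arteriovenous shunting (Protocol IX).

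At stake is a safety decision that precedes 120 further inclusions. The error runs in the unsafe direction, and on that side of the limit no committee is asked.

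**Working it through.** **Inputs.** Unacceptable rate 0.30, expected rate 0.15, n = 35 and limit 7 (Protocol XVI; SAP 5.5.2 and 5.6.2). The number of sunitinib-arm patients without TACE, d, is not given, so a range is shown.

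**Formula.** With n patients assessed, each with event probability p, the probability of a go is P(X ≤ 7) = Σ C(n,k) p^k (1−p)^(n−k), summed over k = 0 to 7. At p = 0.30 this is the false-go risk; at p = 0.15 it is the power.

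**Step 1: the plan's own figures.** For n = 35, P(X ≤ 7) is 0.1326 at p = 0.30 and 0.8562 at p = 0.15. These match the protocol's 13.3% and 85.6%. (SAP 5.5.2 labels the 13.3% two-sided; it is the one-sided exact tail.)

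**Step 2: limit kept at 7, n = 35 − d.**

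| d | n assessed | False-go (p = 0.30) | Power (p = 0.15) |
|---|---|---|---|
| 0 | 35 | 13.3% | 85.6% |
| 1 | 34 | 15.6% | 87.3% |
| 2 | 33 | 18.2% | 88.9% |
| 3 | 32 | 21.2% | 90.4% |
| 5 | 30 | 28.1% | 93.0% |

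As an illustration only, borrowing the 5% loss allowance of phase III gives 0.05 × 35 = 1.75, or about 2 patients, and hence the 18.2% row. No assumption about the event risk of the missing patients is needed: the endpoint is an event within a week of a TACE session, so a patient without TACE cannot have one.

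**Step 3: is the exclusion the cause?** Suppose patients without TACE stay in the 35 as non-events. The event total still comes from the n = 35 − d patients who had TACE, so P(X ≤ 7) is unchanged: 15.6% for d = 1 and 18.2% for d = 2. The cause is therefore the fixed limit without replacement.

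**Step 4: the percentages do not settle it.** Protocol XVI attaches 20% to 7 patients and 22.9% to 8. But 7/34 = 20.6% and 7/33 = 21.2%, both between the two. By count these are a go; by percentage the plan is silent.

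**Step 5: lowering the limit instead.** A limit of 6 gives false-go and power of 7.9% and 75.9% at n = 34, 9.4% and 78.3% at n = 33, and 11.3% and 80.5% at n = 32. False-go is controlled, but 5 to 10 points of power are lost against 85.6%.

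**Step 6: off-drug patients.** Keep all 35, of whom m never took the drug and have risk r, and the rest have 0.30. Summing over both binomials, false-go is 14.4–14.8% for m = 1 and 15.7–16.5% for m = 2 when r is 0.10–0.15 (the protocol's rate for TACE, assumed here to apply). At r = 0.30 nothing changes. At r = 0.35–0.40, m = 1 gives 12.5–12.9%.

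**The case against.** The strongest objection is that the shortfall may be nil. Suitability for TACE is an inclusion criterion, and no document gives a number without it. The 13.3% is a calculated value, not a declared ceiling. SAP 8.4 reports number, percentage and confidence interval by arm, so a smaller denominator would be visible. All of this stands and limits the weight of the point. But the decision rule does not use the visible denominator, and at 7 or fewer nobody is asked to look at it.

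A reader might infer two stronger points.

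- *Dropping patients without TACE is itself wrong.* It is not: they cannot have the event, and keeping them gives the same false-go risk (Step 3).
- *Counting patients who took no sunitinib dilutes the safety test and is an error.* There is text in favour. Protocol XVI says "We defined the unacceptable toxicity rate as 30 % in patients undergoing TACE plus sunitinib treatment" and words H0 as "An occurrence rate of bleeding or liver failure 1 week after last administration of the TACE-sunitinib combination of 30 % is unacceptable". Protocol XVII says of patients with at least one dose: "This will be the population for the analysis of all safety data". Other text points the opposite way. Protocol XVI also says "Analyses of the principal and secondary objectives will be conducted on an intent-to-treat basis and will bear on all of the patients enrolled", SAP 5.5.2 words both hypotheses per chemoembolization session without naming sunitinib, and SAP 5.6.2 applies the limit to the arm. The sentence may also cover patients who stopped the drug before a later TACE, and counting those is cautious. The shift is about 1 to 3 points for one or two patients, and its direction depends on an assumed risk. Restricting the gate to exposed patients would remove events from a safety decision and require exposure to be tracked by arm. The documents support calling this a trade-off, not a mistake.

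**Conclusion.** The point holds in a limited form. The stated 13.3% and 85.6% are correct for 35 assessed sunitinib-arm patients and for no other number. One such patient without TACE takes the false-go risk to 15.6%, and two take it to 18.2%. Power rises slightly, so the whole cost falls on the safety side.

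This rests on a true 30% rate in the assessed patients and on at least one sunitinib-arm patient lacking TACE, which the SAP provides for but does not quantify. The documents do not show that the trial's false-go risk is above 13.3%, only that nothing in the plan keeps it there. Because the rule guards a safety decision and the remedy is cheap, the gap should be closed.

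**What to change.** **Main change (SAP 5.6.2 and 7.2.2).** Continue phase II inclusion, before the suspension planned in SAP 5.6.4, until at least 35 patients per arm have had at least one TACE. Apply the limit of 7 to the first 35 such sunitinib-arm patients in randomisation order, which restores 13.3% and 85.6%. List events in any further patients for the independent committee.

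**Fallback if fewer than 35 are assessed.** Report the actual false-go risk and power beside the decision (15.6% and 87.3% at n = 34; 18.2% and 88.9% at n = 33), and refer a count of exactly 7 to the committee. An automatic go then needs 6 or fewer, with a false-go risk of 7.9% or 9.4%.

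**Leave alone.** Keep off-drug patients in the primary count. At most, add a supporting count in patients who took study drug before a TACE.

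**Cost.** A short protocol amendment is needed, because the 70 patients and the 70/120 split are written into Protocol XVI and SAP 5.5.3. The total stays at 190, since phase II patients carry into phase III. If 1 to 2 patients per arm have no TACE (an assumption), 2 to 4 inclusions move forward from the 120. At 7 to 8 per month (SAP 7.1) that is 2/8 to 4/7 of a month, a delay of about 1 to 2.5 weeks. The randomising data centre would have to count TACE-treated patients by arm, which need not unblind doctor or patient.

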5.7.2 Secondary efficacy criteria

5.7.2.1 RECISTm definition of treatment response

This definition will be used for progression-free survival, disease-free survival and tumor control rate.

Progression of target and non-target lesions will always be measured relative to the inclusion MRI.

- For evaluations following TACE: treatment response will be assessed only for lesions (target and non-target) treated during TACE according to RECISTm criteria. Progression is defined as either a treated lesion that progresses or the appearance of a new hepatic or extrahepatic lesion. Progression related to untreated lesions will not be taken into account with the exception of one case: progression of an untreated lesion that prevents further treatment with TACE (this information will be reported manually by the CRAs).
- For follow-up evaluations (after TACE is completed), response to treatment will be assessed in relation to all lesions, whether treated during TACE or not.

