| Stratifications | 
 • Main tumour diameter $< vs. \geq 5$ cm • Uninodular vs. multinodular • Centre |
| Duration | Accrual duration : 24 months ; overall study duration : 60 months |

I. RATIONALE

Transcatheter arterial chemoembolization (TACE) is widely used for selected patients with isolated or limited hepatocellular carcinoma (HCC) not suitable for surgical resection. Recent randomized trials have demonstrated a survival benefit for patients treated with TACE, by comparison to symptomatic treatment (1-4). TACE is justified by the fact that HCC is one of the most vascularized tumors. Advances in the understanding of the mechanisms underlying HCC development confirm that angiogenesis plays a key role. After TACE, most of the patients will relapse within two years, and this relapse is associated with a tumor re-vascularisation. Especially, Vascular Endothelial Growth Factor (VEGF) has emerged as a prominent factor (5). In patients undergoing TACE, high pre-treatment serum VEGF concentrations are associated with a shorter survival (6, 7). Moreover, VEGF concentrations rise after TACE, probably as a consequence of tumor ischemia, and reach a peak after 1 day (8). In a murine model, VEGF has been demonstrated to play a crucial role in establishment of collateral circulation and reconstruction of blood supply of residual cancer tissue after TACE (9). In human, increase of VEGF levels during the month following TACE was associated with a higher risk of metastatic relapse (10). Altogether, these data suggest that neoadjuvant plus adjuvant therapy by angiogenesis inhibitors could represent a logical way to reduce the risk of relapse after TACE.

Sunitinib malate (SUTENT) is a novel oral multitargeted receptor tyrosine kinase inhibitor that has shown antiangiogenic and antitumor activities. Antiangiogenic properties of sunitinib are based on its action on VEGFR-1, VEGFR-2 and VEGFR-3 (11). Additionally, sunitinib inhibits PDGFR, which is also involved in HCC growth (11-12).

Based on these properties, we postulate that sunitinib might yield clinical benefit when administered before and after TACE in patients with HCC. Sunitinib might interfere with tumor re-vascularisation as well as tumor growth, and reduce the risk of relapse. Additionally, a recent experimental study performed on a glioma model, showed that sunitinib, by improving tumoral hemodynamics and blood flow, increases the delivery of doxorubicin to tumors (13).

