5.7.2.2 Tumor control rates at 3, 6, 9, 12 months

It is defined as the percentage of patients in Complete Response or Partial Response or in stability at the given time.

Patients for whom tumor assessments would not allow classification will be reviewed by a clinician.

Patients who died will be considered uncontrolled.

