5.7.2.3 Progression-free survival (if Phase III not done)

It is defined as the time interval between the date of randomization and the date of first progression or death (regardless of cause). Progression is defined as progression of lesions according to RECISTm criteria, the appearance of a new liver lesion or an extra-hepatic lesion.

Since progress can be documented on the in-process assessments or the monitoring form, the definition in 5.7.2 applies. The dates to be considered are the dates of the CTs.

Live patients without progression will be censored at the date of the last informative examination or at the date of last news if a surveillance sheet is provided not documenting progression or at the point date.

Clinical progressions will not be taken into account, based on the principle that for this type of pathology, a progression in imaging is necessarily associated with a clinical progression.

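### Judging progression always against the inclusion MRI records local regrowth after a response late, or not at all, in PFS, DFS and tumour control (SAP 5.7.2.1)

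*SAP*

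**What the plan says.** SAP 5.7.2.1 fixes the reference scan without exception: "Progression of target and non-target lesions will always be measured relative to the inclusion MRI". It then sets the scope: "This definition will be used for progression-free survival, disease-free survival and tumor control rate". Neither document gives a smallest-size reference, a numerical growth threshold, or a rule for regrowth after a complete or partial response.

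For assessments following a chemoembolization session, SAP 5.7.2.1 gives two routes to an event: "Progression is defined as either a treated lesion that progresses or the appearance of a new hepatic or extrahepatic lesion". For PFS, SAP 5.7.2.3 says: "Progression is defined as progression of lesions according to RECISTm criteria, the appearance of a new liver lesion or an extra-hepatic lesion". That section and SAP 5.7.2.4 (DFS) both refer back to 5.7.2. SAP 5.7.2.3 also closes one other route: "Clinical progressions will not be taken into account". Tumour control is set out in SAP 5.7.2.2: "It is defined as the percentage of patients in Complete Response or Partial Response or in stability at the given time".

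The protocol frames the problem as relapse. Its Rationale states: "After TACE, most of the patients will relapse within two years, and this relapse is associated with a tumor re-vascularisation". Section XVI (Phase III step) defines relapse-free survival as "Time interval between randomization and local or distant relapse or death (all causes"), with no condition that a relapsing lesion must exceed its inclusion size.

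**The concern.** Chemoembolization is expected to shrink or devascularise the treated lesions, and sunitinib is added to limit what happens next. Regrowth of a treated lesion from its smallest size is one of the events of interest. With a reference fixed at inclusion, a patient whose lesion shrank and is growing again has no event while the lesion stays below its inclusion size. In the tumour control rate, the same patient still counts as controlled.

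At stake is whether PFS, DFS and tumour control measure local relapse when it happens. If they do not, all three look better than the clinical course. Any difference between arms in local regrowth among responders would also be poorly captured.

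**Working it through.** No sample size, event count or power figure depends on this rule, so there is no stated figure to reproduce. The check is algebraic.

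**Inputs**
- Reference for progression: the inclusion scan (SAP 5.7.2.1).
- Growth threshold t: not given in either document. Assumed values 0%, 20% and 25%.
- Smallest size reached, as a fraction f of inclusion size: not given. Assumed values 0.7, 0.5 and 0.3.
- Time T for the diameter to double: not given. Assumed values 3, 6 and 12 months.

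**Step 1: size at which progression is declared** (inclusion size = 1)
- SAP rule: 1 + t.
- Smallest-size reference: f(1 + t).
- Ratio: (1 + t) / [f(1 + t)] = 1/f. The threshold cancels.

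For any t of zero or more, the SAP rule needs a size of at least 1. A lesion present at inclusion therefore cannot progress while it is smaller than it was then.

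**Step 2: numbers with t = 20%**

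| f | Declared at, smallest-size reference | Declared at, SAP rule | Ratio 1/f | Regrowth needed under SAP rule, (1 + t)/f |
|---|---|---|---|---|
| 0.7 | 84% of inclusion size | 120% | 1.43 | 1.71-fold |
| 0.5 | 60% | 120% | 2.00 | 2.40-fold |
| 0.3 | 36% | 120% | 3.33 | 4.00-fold |

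With a smallest-size reference the regrowth needed would be 1.2-fold in every row. Varying t changes the last column but not the ratio: for f = 0.3, the regrowth needed runs from 3.33-fold (t = 0%) to 4.17-fold (t = 25%).

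**Step 3: conversion to time**

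With exponential growth in diameter, the delay is T × log2(1/f), again free of t.

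| f | T = 3 months | T = 6 months | T = 12 months |
|---|---|---|---|
| 0.7 | 1.5 | 3.1 | 6.2 |
| 0.5 | 3.0 | 6.0 | 12.0 |
| 0.3 | 5.2 | 10.4 | 20.8 |

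These are delays in months for one lesion, not shifts in median PFS. The effect on PFS also depends on how many patients have local regrowth as their first event, which the documents do not give.

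**Step 4: can another provision catch the event?**
- New lesions and deaths count, but neither is regrowth of a lesion present at inclusion.
- Clinical progression is not counted for PFS.
- Protocol XI schedules liver imaging only until progression. If a site calls regrowth progression and stops scanning, the later SAP threshold may never be observed. The patient could then be censored under SAP 5.7.2.3. This is how a late event can become a missed one.

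**The case against.** The strongest case against the point concerns its scope, and most of it stands.

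- **Not all relapse is affected.** A reader might infer that the rule hides the relapse the trial was set up to study. New hepatic and extrahepatic lesions count whatever the reference scan, and deaths count in PFS and DFS. Only regrowth of lesions already present at inclusion is delayed or missed.
- **Only secondary endpoints are affected.** The phase III primary endpoint is overall survival. Protocol XVI chose it partly because relapse after chemoembolization is hard to date and the usual criteria may not suit. The phase II decision rests on toxicity. That limits the consequences, but difficulty in dating relapse is also a reason for an explicit rule.
- **Arms are compared only if phase III runs** (SAP 5.7.7 and 8.7). Otherwise the endpoints are described by arm, and only the overstatement remains.
- **Complete response is not settled.** A reader might infer that a lesion that vanished and came back is certainly not an event. The SAP does not say whether a reappearing lesion is new, nor whether whole diameter or viable tumour is measured. This case is unspecified rather than clearly missed.
- **The rule may have a purpose.** Sessions are repeated, and one fixed reference avoids resetting the baseline each time. The SAP does not give this reason. A smallest-size reference does not reset upward either, and the argument would not cover follow-up after the last session.

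The mention of RECISTm criteria in SAP 5.7.2.1 and 5.7.2.3 could be read as importing a different reference. If that is intended, it conflicts with the word 'always' and needs reconciling.

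**Conclusion.** The point holds for three secondary endpoints. Applied as written, the rule declares progression of a previously shrunken lesion at 1/f times the size that a smallest-size reference would use: 1.4, 2.0 and 3.3 times for f = 0.7, 0.5 and 0.3. That result needs no assumption about the threshold, only that both rules use the same one. The fractions are illustrative. Delays in months rest on an assumed doubling time and should be quoted only as a range.

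PFS, DFS and tumour control are overstated to the extent that local regrowth after response comes before any other event.

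A reader might infer a bias towards one arm. The documents do not support a direction. The delay grows with depth of response, so an arm that only deepens initial shrinkage would gain apparent PFS, while an arm that prevents regrowth among responders would get little credit for it. No response depth by arm is given, so the net effect on a hazard ratio cannot be computed.

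**What to change.** For the analysis endpoints only, leaving the rules for treatment and its discontinuation untouched, amend SAP 5.7.2.1 as follows:

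- Judge progression against the smallest measurement recorded since inclusion, and keep the inclusion scan as the reference for response.
- State the growth threshold, and whether whole diameter or viable tumour is measured.
- State that reappearance of a lesion after complete response counts as progression.
- Reconcile the fixed inclusion reference with the RECISTm wording in SAP 5.7.2.1 and 5.7.2.3, and with the local relapse component of the protocol's relapse-free survival.
- Retain the present rule as a sensitivity analysis, so that its influence can be seen.

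The cost is small. Protocol XI already schedules imaging one month after each session and every 3 months for 2 years, with independent panel review, and SAP 7.3 allows changes before the database is frozen. The work is re-deriving progression dates from the serial scans. It requires lesion sizes at each assessment; the documents do not confirm that these are recorded, so this should be checked first.
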